The study enrolled 24 participants from two sites: Keelung Hospital and Lover's Lake Hospital. Participants were randomly assigned into two groups via computer-generated randomization, with 12 individuals in the experimental group and 12 in the control group. The experimental group received *Diandao San* ointment, while the control group received a placebo ointment with a similar appearance and scent but without therapeutic effects. Both ointments were applied twice daily to clean skin on the affected areas for six weeks. In cases of adverse skin reactions, application was temporarily halted, and the reactions were documented and monitored.

Assessment and Evaluation

Before enrollment, participants underwent evaluations, including Fitzpatrick skin type classification, distribution of rosacea lesions, severity of erythema, papules, and pustules, and quality of life assessments. Adverse skin reactions were also recorded. Follow-up assessments were conducted at weeks 1, 2, 4, and 6 by TCM practitioners, who re-evaluated skin symptoms, quality of life, and adverse reactions.

- **Skin Type:** Assessed using the Fitzpatrick classification scale.
- **Lesion Distribution:** Documented with photographs, noting affected areas such as bilateral cheeks, nose, chin, forehead, and eyes.
- **Severity of Skin Symptoms:** Assessed using the Investigator Global Assessment (IGA) scale.
- **Quality of Life:** Measured using the Dermatology Quality of Life Index (DQoL), evaluating emotional, symptomatic, and lifestyle impacts.

Participants in the experimental group achieving an IGA and DQoL score of 0-1 after six weeks were considered to have significant improvement and did not require further treatment. Those with IGA scores of 2-3 or DQoL scores between 2-10, showing significant improvement compared to baseline, continued using *Diandao San* ointment. Participants with no significant improvement post-trial were referred to dermatologists and TCM practitioners for alternative treatment options. In the control group, participants experiencing severe adverse reactions, allergic responses, or infections were immediately withdrawn from the study and evaluated for further treatment.

Data Analysis

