Statistical analysis was performed using SPSS software. Baseline differences were analyzed using ANOVA, while paired t-tests were used to compare pre- and post-treatment data. The study assessed all parameters, including mean values and standard deviations, with a significance level set at $\alpha = 0.05$ (one-tailed).

The analysis uses Robust Linear Mixed-Effect Models (LMMs) due to the violation of normality in outcome measurements. To address this issue, robust LMM was applied to enhance the reliability of estimates by mitigating the effects of outliers or non-normal data distributions.

Additionally, the robustlmm method was used, which down-weights outliers by modifying the loss function, ensuring that extreme observations do not disproportionately influence the fixed effect estimates. This approach increases the robustness of estimation methods, improving the accuracy and stability of the results.

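### One-tailed pre-post t-tests stand beside a stated normality violation and a robust model, with no statement of which analysis carries the efficacy conclusion; the t-tests do not compare ointment with placebo

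*Combined protocol and SAP*

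**What the plan says.** The opening paragraph of Data Analysis states that "paired t-tests were used to compare pre- and post-treatment data" and sets a one-tailed significance level of 0.05. The next paragraph says that robust linear mixed models are used "due to the violation of normality in outcome measurements", and that "robust LMM was applied to enhance the reliability of estimates by mitigating the effects of outliers or non-normal data distributions".

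Both analyses stand in the plan. The section does not say:
- which of them is primary, or whether the robust model replaces the t-tests;
- whether the t-tests are run within each arm or on all 24 patients together;
- which fixed effects the mixed model contains;
- how the pre-post differences are distributed. Non-normality is reported for the outcome measurements, and skewness is not mentioned.

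The trial is small: Study Design describes random allocation "with 12 individuals in the experimental group and 12 in the control group". Assessment and Evaluation names the outcomes as skin severity, "Assessed using the Investigator Global Assessment (IGA) scale", and quality of life by the DQoL, with lower scores counted as better on both. It also says: "Follow-up assessments were conducted at weeks 1, 2, 4, and 6 by TCM practitioners".

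**The concern.** The trial randomises patients to ointment or placebo, but the only test that the plan spells out for the effect of treatment compares each patient with his or her own baseline. That comparison makes no use of the placebo arm. Patients can improve over six weeks through regression to the mean, natural fluctuation, or applying any ointment at all. A pre-post test counts all of this as improvement.

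The reported non-normality adds a second doubt. With 12 patients per arm the central limit theorem offers limited protection, and a one-tailed test is the form most exposed to skewness, because an excess in one tail is not offset by a shortfall in the other. The plan adopts a robust method for its data, yet leaves a normal-theory small-sample test in place without explanation.

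If the t-test p-values were used to support efficacy, the trial could report a benefit that the randomised comparison does not show.

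**Working it through.** **Inputs from the documents.** Paired t-test, one-tailed, level 0.05 (Data Analysis); 12 patients per arm (Study Design).

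**Assumed inputs.** Tests run per arm with all 12 patients observed; the size of any change shared by both arms; the shape of the pre-post differences. The documents give none of these, so ranges are shown.

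**Step 1: the plan's own level.** With n = 12 there are 11 degrees of freedom and the one-tailed 5% critical value is t = 1.796. With normal differences and no mean change, simulation (400,000 trials) rejects in 4.99%. The stated 0.05 is reproduced under normality.

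**Step 2: what the test says about ointment versus placebo.** Let both arms improve by the same amount, d SDs of the pre-post differences, so that the ointment adds nothing. With normal differences the ointment-arm statistic follows a noncentral t distribution with 11 degrees of freedom and noncentrality d × √12, where √12 = 3.464. The chance of a significant result is P(T > 1.796).

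| Shared improvement d | Noncentrality | Ointment arm significant |
|---|---|---|
| 0 | 0 | 5% |
| 0.3 | 1.04 | 25% |
| 0.5 | 1.73 | 49% |
| 0.8 | 2.77 | 83% |

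This result needs no departure from normality.

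**Step 3: non-normal scores with symmetric differences.** A paired t-test depends on the distribution of the differences, not of the scores. If pre and post scores share one distribution and are exchangeable, their differences are symmetric however skewed the scores are. Simulated one-tailed size at n = 12, for correlations 0 to 0.8:
- lognormal scores: 3.9% to 4.9%;
- IGA-like scores on an assumed 0-4 scale: 4.1% to 5.3%;
- DQoL-like scores on an assumed 0-30 scale: 4.8% to 4.9%.

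Symmetric heavy-tailed differences (t with 3 degrees of freedom) gave 4.6%. The test holds its level reasonably well in all of these.

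**Step 4: skewed differences.** With gamma-shaped differences centred at zero mean change:

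| Skewness of differences | Tail in direction of skew | Opposite tail |
|---|---|---|
| 0.5 | 3.8% | 6.6% |
| 1.0 | 2.8% | 8.4% |
| 1.4 | 2.2% | 10.0% |
| 2.0 | 1.5% | 12.6% |

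A discrete example agrees. Changes of -1, 0, 1 and 3 with probabilities 0.4, 0.4, 0.1 and 0.1 have mean -0.4 + 0 + 0.1 + 0.3 = 0 and skewness 1.45; the lower tail rejects 13.1% of the time and the upper tail 1.6%.

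**Step 5: direction.** Lower scores are better, so with change taken as post minus pre, improvement is the lower tail. If the few patients who move far get worse, the skew is positive and the improvement test is liberal. If they get better, the skew is negative and the improvement test is conservative.

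**Step 6: alternatives.** Another within-arm test does not solve this. A sign-flip test on the discrete example still rejects about 9% in the liberal tail, and the Wilcoxon signed-rank test also assumes symmetric differences. The same skewed changes compared between two arms of 12 by a two-sample t-test give about 5% (4.8% to 5.0%), because equal skew in the two arms cancels.

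**The case against.** The strongest case for the plan is that it has already dealt with the normality problem. The robust model is introduced for exactly that reason, and the second paragraph of Data Analysis can be read as replacing the normal-theory tests for the outcomes. That reading is possible, but no sentence says so, and the t-tests are never withdrawn or labelled descriptive.

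A reader might infer something stronger: that because normality is violated and the arms are small, the stated 5% is wrong and benefit will be claimed too often. The documents do not support this. They report non-normal measurements, not skewed differences. Step 3 shows that non-normal scores alone can leave the level near 5%, and Step 5 shows that skew can make the improvement test conservative as easily as liberal.

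Per-arm testing is also an assumption. If all 24 patients were pooled, discrete change distributions with skewness 1.17 and 1.45 would give 8.1% to 9.4% in the liberal tail, against 11.1% and 13.1% at n = 12. A pooled test, however, could not separate ointment from placebo at all. Nor do the documents say that a significant arm will be set against a non-significant one.

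These objections limit the skewness argument. They do not touch Step 2.

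**Conclusion.** The point holds in a limited form. It is certain from the text that one-tailed pre-post t-tests stand beside a stated normality violation and a robust model, with no hierarchy between them.

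The weightier consequence is that a pre-post test cannot show that the ointment works better than placebo. Given an equal improvement in both arms of 0.3 to 0.8 SD of the differences, the ointment-arm test is significant in 25% to 83% of trials with no treatment effect. This rests on per-arm testing, 12 observed patients, and an assumed shared improvement.

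The distortion from non-normality is conditional: about 7% to 13% in one tail and 1.5% to 4% in the other if the differences have skewness 0.5 to 2, and near 5% if they are symmetric. Which case applies, and in which direction, cannot be told from the documents.

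The change should be made. It is justified by Step 2 alone and does not depend on any assumption about skewness.

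**What to change.** In Data Analysis:
- Show pre-post change within each arm descriptively (median, range, number of patients improved), without p-values.
- State that the efficacy conclusion rests on the ointment-placebo contrast from the robust mixed model already in the plan, and specify that contrast as the arm-by-time effect at week 6.
- Optionally, add a re-randomisation test of the 12/12 allocation as a check on that contrast.

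The change needs no new data. It is a change of wording, although the section is written in the past tense; if results already exist, they would have to be reported again on this basis.

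The cost is that within-arm statements of significant improvement are lost and the conclusion rests on a demanding comparison. As a guide, a simple one-tailed 5% two-sample t-test with 12 per arm has noncentrality d × √6 on 22 degrees of freedom, where d is the between-arm difference in SDs of the outcome compared. Its power is 60% at d = 0.8 (noncentrality 1.96) and 77% at d = 1.0 (2.45). That limit comes from the size of the trial, and within-arm tests do not remove it.
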